#### **7.3.2. Causal Relationship to Study Drug**

The Investigator’s assessment of causality is based on clinical judgment regarding the reasonable possibility that the Study drug caused the event and may include consideration of some or all of the following factors:

- Possible alternative causes of the AE, including the disease under treatment, co-morbid conditions, other drugs, and environmental factors.
- The temporal association between drug exposure and onset of the AE.
- Whether the clinical or laboratory manifestations of the AE are consistent with known actions or toxicity of the Study drug.
- Whether the AE resolved or improved with decreasing the dose or stopping the Study drug (“dechallenge”) or recurred or worsened upon re-exposure to the Study drug (“rechallenge”).

The causal relationship between the Study drug and the AE will be described using one of the following categories:

- **Not Related:** Evidence exists that the adverse event has an etiology other than the Study drug (such as a preexisting condition, underlying disease, intercurrent illness, or concomitant medication).
- **Related:** A temporal relationship exists between the event onset and administration of the Study drug. It cannot be readily explained by the subject's clinical state or concomitant therapies and appears with some degree of certainty to be related based on the known therapeutic and pharmacologic actions of the drug. In case of cessation or reduction of the dose, the event abates or resolves and reappears upon rechallenge. It should be emphasized that ineffective treatment should not be considered as causally related in the context of adverse event reporting.

### **7.3.3. Clinical Events Committee (CEC)**

A clinical events committee(s) (CEC) has been established with external experts and will adjudicate thromboembolic and major cardiovascular events. If deemed necessary, the same or a different CEC may also be requested to adjudicate other AEs of interest (e.g., for opportunistic infections, herpes zoster, malignancy). To allow for unbiased assessment, the CEC will remain blinded to treatment assignment. A CEC charter will be drafted with descriptions of membership, the scope of the CEC members' responsibilities, adjudication processes, and definitions used to review and assess specific AEs.

## **7.4. AE Reporting and Recording**

### **7.4.1. AE Reporting**

Timely, accurate, and complete reporting and analysis of safety information from clinical trials is crucial for the protection of subjects and is mandated by regulatory agencies. Sponsor has established standard operating procedures in compliance with regulatory requirements worldwide to ensure appropriate reporting of safety information. All clinical trials sponsored by TBPH will be conducted in accordance with these procedures.

### **7.4.2. AE, SAE and AESI Recording**

All AEs, regardless of seriousness, severity, or causal relationship to Study drug, will be recorded from signing informed consent through the last Study visit (or last subject contact in the case of a follow-up telephone call). AEs will be recorded on the AE page of the CRF. SAEs, regardless of relationship to Study drug will be recorded from signing informed consent through the last Study visit (or last subject contact in the case of a follow-up telephone call). Additionally, investigators may report SAEs assessed as related to Study drug through 30 days following the last Study visit (or last subject contact in the case of a follow-up telephone call). All SAEs will be recorded on both the SAE Report Form and the AE page of the CRF and should include the following:

Description of event:

- Signs and symptoms due to a common etiology should be reported as a single diagnosis; for example, cough, runny nose, sneezing, sore throat, and head congestion would be reported as “upper respiratory infection”.
- A diagnosis or description must be as specific and as complete as possible (e.g., “lower extremity edema” instead of “edema”).
- Hospitalization or surgical procedures should not be used as adverse event terms (e.g., if a subject was hospitalized for cholecystectomy due to cholecystitis, the adverse event term should be recorded as cholecystitis, and not as the procedure, cholecystectomy).
- “Death” should not be used as an adverse event term unless the cause of death is unknown. For events with a fatal outcome, the cause of death should be the adverse event term (e.g., if a subject died of an acute myocardial infarction, the adverse event term should be recorded as “Myocardial Infarction” and the event outcome as fatal).

Relationship to Study drug:

The Investigator will make an assessment of the causal relationship of the Study drug to the AE using the guidelines in Section 7.3.2.

Severity:

The severity of the AE will be assessed using the guidelines in Section 7.3.1.

Outcome:

The outcome of AEs will be recorded.

Therapeutic measures:

Measures taken for the treatment or management of the AEs will be recorded.

**7.4.3. SAE and AESI Reporting Timeline**

SAEs and AESIs will be reported to Clinical Safety and Pharmacovigilance within 24 hours of the time the Investigator or his/her designee becomes aware that a SAE or AESI has occurred, whether or not the event is considered to be related to Study drug. If the initial SAE is reported by telephone, a written report signed by the Investigator must be submitted within 24 hours.

The SAE/AESI Report Form must be completed in accordance with the SAE/AESI Report Form Completion Guidelines. If all information on the SAE/AESI Report Form is not available at the time of the initial report, follow-up SAE/AESI reports will be completed and submitted.

To report an SAE or AESI, complete and fax or email the SAE/AESI Report Form to the following:

Theravance Biopharma Clinical Safety and Pharmacovigilance

[REDACTED]

For medical questions regarding an SAE, contact the Sponsor medical monitor by telephone as follows:

Sponsor Medical Monitor Contact Information:

[REDACTED]

For fatal or life-threatening events, also fax copies of hospital case reports, autopsy reports, and other documents when requested. Additional information may be requested from the investigator to ensure the timely completion of accurate safety reports.

An SAE may qualify for reporting to regulatory authorities if the SAE is possibly attributable to the Study drug and is unexpected/unlisted based on the current TD-1473 Investigator's Brochure. In this case, all investigators will receive notification of the event. The investigator is responsible for notifying the Institutional Review Board or Ethics Committee and documenting the notification, as required by local regulatory authorities and in accordance with the local institutional policy.

### **7.5. Adverse Event Follow-up**

A subject experiencing an AE or SAE or AESI will be followed by the investigator or his/her trained delegate(s) through the follow-up visit or until the investigator and/or the Sponsor has determined that the AE or SAE or AESI has resolved or a stable clinical endpoint is reached, whichever is longer. The Sponsor may request follow-up of certain adverse events until resolution and documentation of assessments made during this period.

The investigator must take all therapeutic measures necessary for resolution of an SAE or an AESI. Any medications necessary for treatment of the SAE or AESI must be recorded in the concomitant medication section of the case report form.

## **8. STATISTICAL CONSIDERATIONS**

### **8.1. General Considerations**

All individual data will be listed as measured. All statistical summaries and analyses will be performed using [REDACTED]

Continuous data will be summarized using an 8-point descriptive summary (*n*, mean, standard deviation, median, interquartile range [25% quartile, 75% quartile]), minimum, and maximum) or a 7-point descriptive summary (*n*, mean, SD, coefficient of variation [CV], median, minimum, and maximum) unless otherwise specified.

Categorical data will be summarized using counts and percentages. Percentages will be shown to 1 decimal place and percentages for zero counts will be omitted.

The Statistical Analysis Plan (SAP) and the table, figure, and listing shells will be finalized prior to database lock. Any changes to protocol-specified analyses will be described in the SAP.

### **8.2. Sample Size**

The sample size will depend on the number of subjects who are eligible and elect to enter from the Maintenance Study of Protocol 0157. It is anticipated that approximately 500 subjects will receive TD-1473 for up to 156 weeks (3 years).

### **8.3. Analysis Sets**

#### **8.3.1. Analysis Sets**

The Safety analysis set, comprising all subjects receiving at least one LTS dose of TD-1473, will be the analysis set for all summaries except some enrollment summaries.

#### **8.3.2. Examination of Subgroups**

Subgroups to be defined in detail in the SAP for safety analysis purposes will include the following:

- Males, females
- Subgroups defined by age category, e.g., under 40 years of age, 40 to 64, 65 and over
- Subgroups defined by geographic region, e.g., North America, Europe, other
- Subgroups defined by steroid use

Subgroups may also be defined in the SAP for efficacy endpoint summaries.

### 8.3.3. Major Protocol Analysis Deviations

The following protocol deviations are considered major and as having (unless rare) a substantial effect on the interpretation of efficacy or safety results:

- [REDACTED]
- [REDACTED]
- [REDACTED]

Additional criteria may be specified in the SAP. Listings of all protocol deviations and of major analysis protocol deviations, as defined above and in the SAP, will be provided.

## 8.4. General Analyses

### 8.4.1. Demographics and Baseline Characteristics

Demographic and baseline characteristics including age, sex, race, ethnicity, creatinine clearance, weight, body mass index (BMI), UC characteristics, current UC medications by category, and other medical history will be summarized.

### 8.4.2. Disposition

An enrollment summary will be provided showing the following counts by previous study treatment and clinical status at enrollment:

- Number of subjects eligible to enroll
- Number who elected to enroll
- Number who received at least one LTS dose

Enrollment will also be summarized for subjects in the Safety analysis set by region and country, and by site, ordering sites by descending number of subjects dosed.

For subjects in the Safety analysis set, a disposition summary will present the following counts:

- Number of subjects who completed the Week 4 visit
- Number who completed the Week 12 visit
- Number who completed the Week 52 (1-yr) visit
- Number who completed the Week 104 (2-yr) visit
- Number who completed the Week 156 visit
- Number who discontinued from the study prior to the Week 156 visit, overall and by reason for discontinuation

Subjects who discontinue study drug prior to the Week 156 visit will complete an End of Study visit 4 weeks after their last dose of study drug.

[REDACTED]

[REDACTED]

[REDACTED]

[REDACTED]

[REDACTED]

[REDACTED]

[REDACTED]

[REDACTED]

[REDACTED]

[REDACTED]

[REDACTED]

[REDACTED]

[REDACTED]

[REDACTED]	[REDACTED]	[REDACTED]
[REDACTED]	[REDACTED]	[REDACTED]
[REDACTED]	[REDACTED]	[REDACTED]
[REDACTED]	[REDACTED]	[REDACTED]

[REDACTED]	[REDACTED]	[REDACTED]
[REDACTED]	[REDACTED]	[REDACTED]
[REDACTED]	[REDACTED]	[REDACTED]
[REDACTED]	[REDACTED]	[REDACTED]
[REDACTED]	[REDACTED]	[REDACTED]
[REDACTED]	[REDACTED]	[REDACTED]

[REDACTED]

## 8.6. Safety Analyses

Safety variables to be summarized include vital signs, adverse events, clinical laboratory results (hematology, chemistry, overnight fasting lipid panel), and 12-lead ECG intervals, including QT interval corrected for heart rate using Fridericia's formula (QTcF).

### 8.6.1. Adverse Event Data

Adverse events will be coded using the Medical Dictionary for Regulatory Activities (MedDRA®). Summaries will present by system organ class (SOC), preferred term (PT), and severity, the number and percentage of subjects reporting each observed event.

A treatment-emergent adverse event (TEAE) is defined as any AE with a recorded start date on or after the date of the first dose of LTS study drug up through 4 weeks after the last dose of study drug. Treatment-emergent status of AEs with a partial start date will be determined using available date information. If the available date information is inconclusive or no date information was recorded, the AE will be classified as LTS treatment-emergent.

All TEAEs will be listed by subject, and a separate listing of AEs classified as not LTS treatment-emergent (i.e., ongoing at entry) will be provided. Numbers of subjects who experienced TEAEs will be summarized overall and by arm. TEAEs will also be summarized by relationship to treatment (study drug) and severity, and by duration of exposure categories to be specified in the SAP.

A listing will be provided for all subjects who experience an SAE. Listings will also be provided for subjects who discontinued study treatment because of AEs, subjects who temporarily interrupted study treatment because of AEs, and subjects who experienced AESIs.

### **8.6.1.1. Adverse Events of Special Interest**

A summary will be provided showing, overall and by arm, numbers of subjects who experienced events in each of the following categories:

- Suspected or confirmed intestinal perforation
- Complicated herpes zoster (multi-dermatomal, disseminated, or with ophthalmic or CNS involvement)
- Malignancy excluding non-melanoma skin cancer
- Non-melanoma skin cancer
- Serious infection (e.g., that requires hospitalization or intravenous antibiotics)
- Opportunistic infections
- Thromboembolic disease (e.g., deep vein thrombosis, pulmonary embolism)
- Clinical laboratory abnormalities of concern (Refer to Section 7.2)
- Major cardiovascular event (e.g., myocardial infarction or cerebrovascular accident)

For events in each category for which at least one event was reported, a time-to-event plot will be provided. Time 0 will be the time of the first TD-1473 dose, rather than the time of the first LTS TD-1473 dose.

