### 3. STUDY DESIGN

#### 3.1. Overview

This LTS Study 0164 is designed to evaluate the safety of long-term TD-1473 treatment in subjects with moderate to severe UC rolling over from Protocol 0157.

Subjects eligible for the study are those who are rolling over from Protocol 0157 Maintenance Study who meet all inclusion and no exclusion criteria, including having achieved clinical response during an Induction Study and during the Maintenance Study who:

- a) demonstrate persistent [REDACTED] loss of response (no improvement for approximately 6 to 8 weeks after meeting loss of response criteria despite more time on study drug and potentially concurrent rescue medication  
**OR**
- b) have (two) Clinical Flares after an episode [REDACTED] of loss of response during the Maintenance Study  
**OR**
- c) complete the Maintenance Study and confirmation of clinical remission status results are available [REDACTED]

Refer to Protocol 0157 with regards to for additional information related to the Study design. Subjects are required to enter the LTS Study within 14 days of exiting the Maintenance Study of Protocol 0157.

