## 4. STUDY POPULATION

### 4.1. Inclusion Criteria

To be eligible for the study, subjects are required to enter the LTS Study within 14 days of exiting the Maintenance Study of Protocol 0157 and must meet all the following criteria:

Capable of providing informed consent, which must be obtained prior to any study-related procedures.

1. One of the following:
  - a. Those who demonstrated persistent [REDACTED] loss of response (no improvement approximately 6 to 8 weeks after meeting loss of response criteria)  
**OR**
  - b. Two Clinical Flares after an episode [REDACTED] of loss of response during the Maintenance Study.  
**OR**
  - c. Those who have completed the Maintenance Study [REDACTED] and have a confirmed clinical remission status (in remission or not in remission) with available results.
2. During the study and for 7 days after receiving the last dose of the study drug, females of childbearing potential or men capable of fathering children must agree to use highly effective birth control measures (failure rate <1% when used consistently and correctly) or agree to abstain from sexual intercourse. Females of childbearing potential must test negative for pregnancy at Day 1. (Refer to Section 4.3).
3. All male subjects must agree to refrain from semen donation during the study and for 7 days after the last dose of study drug.
4. Must be able and willing to adhere to the study visit schedule and comply with other study requirements.

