**Coexisting medical conditions or past medical history:**

6. Deemed by the investigator to be inappropriate for this study; or has any condition which would confound or interfere with the evaluation of the safety or tolerability of the study drug [e.g., developed unstable or uncontrolled and clinically significant allergic (except for untreated, asymptomatic, seasonal allergies), hematological, endocrine/metabolic, coagulation, immunologic, pulmonary, cardiovascular, hepatic (except hepatic steatohepatitis), GI (except UC), genitourinary, psychiatric, oncologic thrombotic (e.g., deep vein thromboses (DVT) or pulmonary embolism or neurological disease or other medical disorder before during or after Protocol 0157)]; or is unable or unwilling to comply with the study protocol.
7. Develops hypersensitivity to excipients or contents of the study drug as noted in Protocol 0157.
8. Participating in or interested in participating in another investigational study (exception Protocol 0157)
9. Has clinically significant abnormalities in the results of laboratory evaluations at the most recent laboratory evaluation prior to LTS Day 1 visit as determined by the investigator, including:
  - AST, ALT, or alkaline phosphatase  $\geq 2x$  the upper limit of normal (ULN)
  - Total bilirubin  $> 2x$  ULN (unless diagnosis of Gilbert's syndrome)
  - Creatinine clearance as calculated by the Cockcroft-Gault formula  $< 30$  mL/min (Refer to [Appendix 2](#))
  - Total white blood cell count (WBC)  $< 3 \times 10^9/L$
  - Absolute neutrophil count  $< 1.5 \times 10^9/L$
  - Absolute lymphocyte count  $< 0.8 \times 10^9/L$
  - Hemoglobin  $< 8$  g/dL
  - Platelet count  $< 100 \times 10^9/L$ .
10. Subject has had a live viral vaccine (e.g., MMR, varicella zoster, herpes zoster, oral polio virus, FluMist®, attenuated typhoid fever vaccine, attenuated rotavirus vaccine, yellow fever vaccine, or any investigational live vaccine) within 4 weeks prior to Day 1 and/or is unwilling or unable to avoid live viral vaccines during the Study and for 8 weeks following the last dose of study drug. Subject must be willing to avoid contact with any

household member who has been vaccinated with a live attenuated vaccine within 2 weeks after vaccination.

11. Are pregnant, lactating, breastfeeding or planning to become pregnant during the Study or within 7 days after the last dose of Study Drug

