5. SUPPORTING DOCUMENTATION

5.1. Appendix 1: Changes to Protocol-Planned Analyses

The protocol-planned efficacy analyses are not required for the synoptic CSR.

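### The AESI time-to-event plots run from the first TD-1473 dose but include only subjects who reached the LTS; without a delayed-entry rule, an ordinary curve understates risk by time since first dose

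*Protocol*

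**What the plan says.** Four statements in the protocol bear on the AESI plots.

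- **Time origin (8.6.1.1).** "Time 0 will be the time of the first TD-1473 dose, rather than the time of the first LTS TD-1473 dose". A plot is planned for every AESI category with at least one reported event.
- **Population (8.3.1).** "The Safety analysis set, comprising all subjects receiving at least one LTS dose of TD-1473, will be the analysis set for all summaries", apart from some enrollment summaries. SAP section 2 repeats this.
- **Events (8.6.1).** A TEAE is "any AE with a recorded start date on or after the date of the first dose of LTS study drug", up to 4 weeks after the last dose.
- **Route into the set (3.1, 4.1, 4.2).** Subjects come through 0157, "including having achieved clinical response during an Induction Study and during the Maintenance Study", and "subjects are required to enter the LTS Study within 14 days of exiting the Maintenance Study of Protocol 0157". Exclusion 6 keeps out, among others, anyone who in the investigator's judgement "has any condition which would confound or interfere with the evaluation of the safety or tolerability of the study drug"; its examples include cardiovascular, oncologic and thrombotic disease.

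No visible text names the estimator, lets subjects join the risk set late, adds 0157 subjects who did not roll over, or adds a second plot from LTS Day 1.

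SAP section 3.4.2.1 plans AESI incidence overall, by category and by preferred term, and says nothing about a plot. SAP Appendix 1 declares one change from the protocol: "The protocol-planned efficacy analyses are not required for the synoptic CSR". Figure specifications are in a separate document that is not available.

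**The concern.** The origin and the population do not match. For a subject exposed to TD-1473 in 0157, the time from first dose to first LTS dose is time that the subject had to get through in order to be plotted. A subject whose AESI in that interval prevented rollover is absent. This is left truncation: if the time is counted as time at risk, it is immortal time. The denominator grows by person-time in which these subjects could not have had a disqualifying event, and the curve sits too low.

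Safety is the primary objective, and these plots are the only display of AESI timing that the visible protocol text plans. A reader would take the curve as the risk of, say, thromboembolism by a given time since first exposure. Drawn in the ordinary way, it does not show that.

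**Working it through.** The documents give no AESI rate, no expected number of AESIs and no length of stay in 0157. There is thus no figure of the plan's own to reproduce, and everything below is illustration.

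**Inputs from the documents:** the origin, population and event rules above; up to 156 weeks (3 years) of LTS treatment; about 500 subjects anticipated.

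**Assumed inputs:** constant hazard *h*; time *E* from first TD-1473 dose to LTS entry; LTS follow-up *F*; all entrants exposed to TD-1473 in 0157; events counted only from the first LTS dose; no delayed entry.

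**1. Crude rate**

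Events per subject = 1 − exp(−hF). LTS person-time per subject, P = (1 − exp(−hF))/h. Diluted rate = events/(E + P). Ratio to the true rate = P/(E + P).

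With h = 0.03 per year (3 per 100 patient-years):

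- F = 1 year: events = 1 − exp(−0.03) = 0.02955; P = 0.985.
- F = 3 years: events = 1 − exp(−0.09) = 0.08607; P = 2.869.

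| E (years) | F = 1: rate per 100 PY | ratio | F = 3: rate per 100 PY | ratio |
|---|---|---|---|---|
| 0.3 | 0.02955/1.285 = 2.30 | 77% | 0.08607/3.169 = 2.72 | 91% |
| 0.5 | 0.02955/1.485 = 1.99 | 66% | 0.08607/3.369 = 2.55 | 85% |
| 1.0 | 0.02955/1.985 = 1.49 | 50% | 0.08607/3.869 = 2.22 | 74% |

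Neither document plans a rate per person-year. The rate serves only to show how much the extra time at risk dilutes the events.

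**2. Height of the curve**

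With h = 0.03 and E = 1.0 year for everyone, the curve 2 years after first dose has accumulated only one year of hazard: 1 − exp(−0.03) = 3.0%. The true two-year risk is 1 − exp(−0.06) = 5.8%.

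**3. Simulated Kaplan-Meier curves**

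Setting: 500 entrants, 300 replicates, assumed hazard 2 per 100 patient-years, 156 weeks of LTS follow-up, no delayed entry. True risk since first dose is 1.98% at week 52 and 3.92% at week 104.

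| Time in 0157 since first dose | Share exposed in 0157 | Curve at week 52 | Curve at week 104 |
|---|---|---|---|
| 8–16 weeks | 100% | 1.54% | 3.44% |
| 16–52 weeks | 100% | 0.69% | 2.67% |
| 16–52 weeks | 70% | 1.05% | 3.05% |
| 52 weeks | 100% | 0.00% | 1.96% |

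In the same simulations, a clock started at LTS entry gave 1.90% to 2.00% at 52 weeks and 3.82% to 3.97% at 104 weeks. That recovers the assumed hazard.

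**4. If AESIs that entrants had in 0157 are also plotted**

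The documents do not say whether they are. If so, the early part of the curve is not strictly flat. Subjects whose AESI prevented rollover are still missing, so as long as there are some, the curve is still too low. The figures above would then overstate the shortfall.

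**The case against.** The strongest reply is that section 8.6.1.1 fixes only a time origin. It names no estimator and no risk-set rule, and protocol 8.1 leaves detail to the SAP and the figure shells. Delayed entry on the first-dose scale is compatible with the sentence. That scale is also a sensible choice for events with latency, such as malignancy. All of this is fair. But with the stated origin and population and no entry rule, the default curve is the biased one, and nothing visible tells the programmer to do otherwise.

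Stronger readings are tempting, and the documents do not support them:

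- **That the plot is certain to be produced because SAP Appendix 1 drops only efficacy.** That appendix is not exhaustive: SAP 3.2.1 and 3.5.2 also drop the enrollment and subgroup summaries, which the appendix omits. The SAP plans AESI incidence only, for a synoptic report after early termination. The plots may simply have been left out without a record.
- **That the curve must be flat over the 0157 period.** The plot rule speaks of events in each category, not expressly of TEAEs, and AEs may be carried over from 0157 (protocol 6.4.1.3).
- **That exclusion 6 removes everyone with an earlier oncologic or thrombotic event.** It is judged by the investigator, and its examples are limited to unstable or uncontrolled and clinically significant disease. Some subjects with an earlier AESI, such as a resolved infection, could enter.
- **That the bias differs between dose arms.** This would require entrants with no TD-1473 before the LTS. Some came from placebo in Maintenance (SAP 1.2), but the documents do not say whether they had TD-1473 in Induction. The phrase about arms in 8.6.1.1 attaches to the counts, not expressly to the plots.
- **That the study understates AESI risk in general.** Counts, incidence and listings do not use this clock.

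**Conclusion.** The point holds for the plots. As the protocol stands, an ordinary time-to-event curve would count pre-LTS time as time at risk in a set that excludes anyone whose AESI prevented rollover, and would understate risk by time since first TD-1473 dose. It applies only to entrants exposed in 0157; for anyone first dosed in the LTS the two origins coincide.

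The direction follows from the text. The size does not: the range of 50% to 77% of the true rate at 1 year of LTS follow-up, and 74% to 91% at 3 years, rests on the assumed hazard, earlier exposure and counting rule. Actual follow-up is not given. The study was terminated early, and shorter LTS follow-up makes the dilution worse.

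One descriptive display is affected, and the SAP does not mention it. I rate this as minor, rising to a change that should be made if the plots are produced, with moderate confidence.

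**What to change.** State in SAP 3.4.2.1 whether the AESI plots are kept.

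**If kept, choose one of these:**

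1. Set Time 0 at the first LTS dose. The curve then shows risk since LTS entry among entrants.
2. Keep the scale from first TD-1473 dose, but let each subject join the risk set at the first LTS dose and count only events from then. Show numbers at risk, and describe the curve as conditional on event-free rollover. The small downside is that few or no subjects are at risk early on this scale, so the early part is unstable or empty. If all subjects entered at about the same time since first dose, the curve would say nothing about risk before that time.

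**If dropped,** list the removal in SAP Appendix 1, since protocol 8.1 requires changes to protocol-specified analyses to be described in the SAP. SAP section 1 says that the appendices are not a formal part of the signed plan, so one line in 3.4.2.1 as well would be prudent.

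The cost is a sentence in the SAP and, for option 2, an entry-time variable. The first-dose dates are needed for the plot in any case, so no new data have to be collected.
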